### **2.6.3 Handling of intercurrent events**

For NEDA clinical in Months 6 to 18 and NEDA radiological in Months 6 to 18, the same approach outlined for NEDA-3 in [Section 2.5.3](#) will be followed. For all other secondary endpoints, there is no imputation of missing data planned for this study.

### **2.6.4 Handling of missing values not related to intercurrent event**

For NEDA clinical in Months 6 to 18 and NEDA radiological in Months 6 to 18, the same approach outlined for NEDA-3 in [Section 2.5.4](#) will be followed. For all other secondary endpoints, there is no imputation of missing data planned for this study.

### **2.6.5 Sensitivity analyses**

There are no sensitivity analyses of secondary endpoints planned for this study.

### **2.6.6 Supplementary analyses**

There are no supplemental analyses of secondary endpoints planned for this study.

## **2.7 Safety analyses**

Analysis of safety endpoints supports secondary objectives.

### **2.7.1 Adverse events (AEs)**

Adverse events (AEs) will be coded using MedDRA terminology. The MedDRA version used for reporting the study will be indicated in a footnote on relevant outputs.

For reporting purposes, summary tables for AEs will summarize only the following events for ofatumumab-treated participants and healthy control participants:

- On-treatment events (treatment-emergent AEs), which started or worsened on or after the date of the first dose of ofatumumab for ofatumumab-treated participants
- On-study events, which started or worsened on or after the date of the date of Week 0 visit for healthy control participants

The number and percentage of participants with treatment-emergent/on-study AEs will be summarized for the open-label treatment phase, open-label extension period and overall, in the following ways using the SAF or HCAS, as appropriate:

- by Cohort, primary SOC and PT
- by Cohort, primary SOC, PT and maximum severity
- by Cohort and PT

Separate summaries will be provided using the SAF or HCAS, as appropriate, for treatment-emergent/on-study AEs occurring with a frequency of >5% in either Cohort, treatment-related AEs (only applicable to ofatumumab-treated participants), AEs leading to study drug interruptions (only applicable to ofatumumab-treated participants), serious adverse events (SAEs), treatment-related SAEs (only applicable to ofatumumab-treated participants) and other significant AEs leading to discontinuation.

In addition, an overview of treatment-emergent/on-study AEs will be summarized for the open-label treatment phase, open-label extension period and overall, presenting the number and percentage of participants having at least one AE for each of the categories described above.

If a participant reported more than one AE with the same PT, the AE with the greatest severity will be presented. A participant with multiple AEs within a primary SOC is only counted once towards the total of the primary SOC.

Partial AE start and end dates will be imputed as outlined in [Section 5.1.2](#).

For the legal requirements of ClinicalTrials.gov and EudraCT, two required tables on on-treatment/treatment-emergent AEs which are not SAEs with an incidence greater than 5% and

on on-treatment/treatment-emergent SAEs and SAEs suspected to be related to study treatment will be provided by SOC and PT on the SAF.

If for a same patient, several consecutive AEs (irrespective of study treatment causality, seriousness and severity) occurred with the same SOC and PT:

- A single occurrence will be counted if there is  $\leq 1$  day gap between the end date of the preceding AE and the start date of the consecutive AE
- More than one occurrence will be counted if there is  $> 1$  day gap between the end date of the preceding AE and the start date of the consecutive AE

For occurrence, the presence of at least one SAE/SAE suspected to be related to study treatment/non-SAE has to be checked in a block e.g., among AEs in a  $\leq 1$  day gap block, if at least one SAE is occurring, then one occurrence is calculated for that SAE.

The number of deaths resulting from SAEs suspected to be related to study treatment and SAEs irrespective of study treatment relationship will be provided by SOC and PT.

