Treatment arm/group	A treatment arm/group defines the dose and regimen or the combination, and may consist of 1 or more cohorts
Treatment of interest	The treatment of interest and, as appropriate, the alternative treatment to which comparison will be made. These might be individual interventions, combinations of interventions administered concurrently, e.g. as add-on to standard of care, or might consist of an overall regimen involving a complex sequence of interventions. This is the treatment of interest used in describing the related clinical question of interest, which might or might not be the same as the study treatment
Variable (or endpoint)	The variable (or endpoint) to be obtained for each participant that is required to address the clinical question. The specification of the variable might include whether the participant experiences an intercurrent event
Victim drug	The drug that is affected by the drug-drug interaction
Withdrawal of study consent (WoC) / Opposition to use of data / biological samples	Withdrawal of consent from the study occurs when the participant explicitly requests to stop use of their data and biological samples (opposition to use data and biological samples) AND no longer wishes to receive study treatment AND does not agree to further protocol required assessments. This request should be in writing (depending on local regulations) and recorded in the source documentation. Opposition to use data/biological samples occurs in the countries where collection and processing of personal data is justified by a different legal reason than consent

Amendment 03

Rationale for Amendment

The purpose of Amendment 3 is to make editorial modifications and amend study design items that required updates to provide further clarification.

Changes throughout protocol:

- [REDACTED]
- [REDACTED]
- Updated contraception options to include a single barrier method as acceptable
- Updated figure 3-1 to clarify 2 distinct time periods for healthy control arm since reconsenting after the first 18 months will be required
- Clarification on use of plasmapheresis for the treatment of a relapse
- Clarified MRI timeframe and Migraine criteria

[REDACTED]

Amendment 02.01

Rationale for Amendment

Administrative change on the protocol cover page 1 and the protocol summary page 17, to update the protocol title to reflect the trial phase (Phase IV):

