Purpose	To complement the ofatumumab clinical development pivotal trials by demonstrating clinical and MRI efficacy (both conventional and non-conventional) in a young adult, treatment naïve, very early MS patient population; patients earlier in the MS disease continuum than those in ASCLEPIOS I and II.
Primary Objective(s)	The primary objective is to explore the impact of ofatumumab (OMB) on the ability to achieve No Evidence of Disease Activity (NEDA-3) status in treatment-naïve, very early RRMS patients over an 18-month, open-label study period after a re-baseline of MRI at 6 months.
Secondary Objectives	
Secondary objectives: Secondary objectives include additional efficacy outcomes after treatment with ofatumumab in a very early RRMS population, as well as comparison to HC on non-conventional MRI measures and adverse events.
 
 • Evaluate the effect of ofatumumab on various clinical (NEDA, disability, relapse) metrics • Evaluate the efficacy of ofatumumab on conventional MRI metrics • Evaluate the efficacy of ofatumumab on patient reported outcomes (PROs) (NeuroQOL™, Patient Determined Disease Steps [PDDS]) • Evaluate the effect of ofatumumab vs healthy controls on whole brain and regional atrophy • Evaluate the safety and tolerability of ofatumumab
	

	
█ [REDACTED]█ [REDACTED]█ [REDACTED]█ [REDACTED]█ [REDACTED]█ [REDACTED]█ [REDACTED]
Study design	
The study is an open-label, multi-center, prospective 18-month study in 118 MS patients with early RRMS (defined as within 6 months of diagnosis of clinically definite RRMS) and who are treatment naïve. RRMS patients will be benchmarked against age- and sex-matched healthy controls (n=50) for select secondary [REDACTED]. Primary analysis will be conducted at Month 18. MRI data will be re-baselined at Month 6 to account for treatment-related pseudo atrophy. Additional efficacy and safety assessments will be evaluated during an optional 12-month open-label extension period to further elucidate the long-term clinical and radiological effect of ofatumumab.

Rationale	
The proposed study would provide rigorous clinical, MRI, digital and biomarker data demonstrating the efficacy, safety and tolerability of ofatumumab in a naïve RRMS population at first diagnosis and would provide the first data relative to healthy controls, identified data gaps in the US.

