1.2 Purpose

This study is meant to complement the ofatumumab clinical development pivotal trials by demonstrating clinical and MRI efficacy (both conventional and non-conventional) in a young adult, treatment naïve, very early MS patient population. The focus will be on patients earlier in the MS disease continuum than the average patient studied in ASCLEPIOS I and II. The baseline characteristics for ASCLEPIOS I and II included: mean ages of 38.9 years and 38.0 years, mean duration from first symptoms of 8.36 years and 8.2 years, and mean EDSS scores of 2.97 and 2.90 years, respectively. In the ASCLEPIOS I and II studies, only ~30% of ofatumumab patients were treatment-naïve and ~24% were under the age of 30, leading to an

identified data gap for ofatumumab in the United States for the treatment of young adult, treatment naïve and very early MS patients (Hauser et al., 2020).

Because the ASCLEPIOS I and II studies had relatively small numbers of treatment-naïve patients compared to similar regulatory trials for competitor products and did not specifically address the very early MS patient population, the current proposed study intends to address these groups. The ASCLEPIOS I and II trials used an active comparator (as required by regulatory authorities) and therefore did not compare ofatumumab to healthy control (HC) patients. This type of HC comparator data can provide important information on safety outcomes (e.g., infections) and the ability of ofatumumab to normalize CNS pathology as measured by biomarkers and MRI. Additionally, there remains a data gap for patient reported outcomes (PRO), digital monitoring and biomarker work, which was either not or incompletely addressed in the ASCLEPIOS study program.

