There are 3 periods to this trial: Screening (up to 4 weeks), open-label active treatment (from Baseline to month 18), and optional 12-month open-label extension (from month 18 to 30).

For participants who discontinue study treatment and study participation prematurely for any reason before the end of the treatment phase, an End of Study visit must be performed within 7 days of study discontinuation.

Upon completing the trial, study patients can continue ofatumumab therapy on commercial drug.

Safety follow-up:

The Safety follow-up (FU) period will be applicable for the following participants:

- participants who complete the Treatment period on the study drug and do not continue on any MS DMT.
- participants who prematurely discontinue study drug and study participation, and do not continue on any MS DMT.

All Safety FU visits must be scheduled relative to the End of Study (EOS) Visit.

Any RRMS patient starting another MS DMT post-trial discontinuation will not have a FU visit performed.

All patients who elect to not be included in the 12-month extension will be followed for an additional 100 days following the EOS timing for that individual patient. A shorter follow-up time is acceptable if patients select a different approved MS DMT (injectable, infusion or oral) treatment during this period. Patients who do not have access to commercial drug within one day of the EOS Visit must continue into the safety FU phase until they are able to access commercial drug or decline DMT therapy moving forward (up to 100 days maximum).

Safety assessments will include standard clinical laboratory evaluations (hematology), [REDACTED], adverse event, and serious adverse event monitoring. Participants that elect to not continue on a DMT after study and have low levels of quantitative

[REDACTED]

serum immunoglobulins during treatment, especially in patients with opportunistic or recurrent infections, should have immunoglobulins monitored by the trial site until B-cell repletion occurs.

4 Rationale

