O = Ofatumumab participant

H = Healthy Control

X = assessment to be recorded in the clinical database or received electronically from a vendor

S = assessment to be recorded in the source documentation only

■ [Redacted]

² Relapse assessment will be performed in scheduled, as well as unscheduled visits as deemed necessary by the Investigator or designee. Assessment can be done on site or via remote procedures

³ Urine β-hCG will be conducted monthly, at home, as well as, at defined clinical visits (scheduled and unscheduled)

[Redacted]

⁴ Assessment during an unscheduled visit will be performed as deemed necessary by the investigator, **except** for vital signs and evaluation of AE, which are mandatory at each visit

⁶ Participants are not required to come to the study site. Remote contact with participants, by site staff around the time of at-home, self-administration of ofatumumab should query about any new or worsening symptoms warranting an unscheduled visit, MS relapse, compliance with study treatment [REDACTED], adverse events, and compliance with contraception requirements (when applicable). The method of contact can be via telephone, email, video conference or text message depending on the preference of each participant

⁷ For the first injection, vital signs should be obtained 30-60 minutes before sc injection and again approximately 60 minutes post-injection

⁸ All lab assessments should be taken prior to dosing at the Day 1 visit. For any later biomarker visits, if the visit coincides with the day the monthly injection is scheduled, the subject should not take the injection in the morning before coming to the site so that the biomarker sample can be drawn before the injection

⁹ Labs must be drawn to allow adequate time for results to be obtained before first study drug administration to ensure participant's eligibility

¹⁰ Urine dipstick: If abnormal send full urinalysis to central laboratory

¹² Data for safety follow-up visit will be captured in source documentation only. Safety follow-up participants are not required to come to study site and lab assessments should be done locally

¹³ Only for participants continuing onto the 12-month open-label extension period

¹⁴ Gadolinium will not be given to healthy controls and gadolinium enhanced T1 MRI imaging will not be conducted in healthy controls

¹⁵ The C-SSRS must be administered at either screening or baseline, then at every on-site visit thereafter until End of Study (EOS)

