## Study duration

Study duration in days will be calculated as follows:

- [(date of last contact/EOS – date of first dose of ofatumumab) + 1] for ofatumumab-treated participants
- [(date of last contact/EOS – date of Week 0 visit) + 1] for healthy control participants

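### The final overall adverse-event percentages by cohort are not adjusted for follow-up, so equal event rates will look unequal if extension uptake or dropout differs between ofatumumab and healthy controls

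*SAP*

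**What the plan says.** SAP 2.7.1 plans adverse-event (AE) tables by cohort in which the "number and percentage of participants with treatment-emergent/on-study AEs will be summarized for the open-label treatment phase, open-label extension period and overall". Ofatumumab participants are counted on the safety set and controls on the healthy control set. SAP 2.2 defines these as everyone who received study drug and every enrolled control, so people who never enter the extension stay in the overall denominators. SAP 2.1 takes the final analysis through Month 30. A further summary is restricted to "treatment-emergent/on-study AEs occurring with a frequency of >5% in either Cohort". The visible text contains no person-time rate and no time-to-first-event method for AEs.

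Protocol section 3 sets an 18-month treatment phase and an optional 12-month extension. Table 8-1 schedules a second consent at Month 18 for both cohorts, qualified by footnote 13: "Only for participants continuing onto the 12-month open-label extension period". It also schedules AE collection in both cohorts up to Month 30.

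The Protocol summary describes the secondary objectives as including "comparison to HC on non-conventional MRI measures and adverse events". Protocol 1.2 gives the reason: "This type of HC comparator data can provide important information on safety outcomes (e.g., infections".

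SAP 2.4.1 summarises study duration and treatment-phase duration by cohort, but neither enters the AE percentages. SAP 2.6.2, by contrast, divides relapses and new or enlarging T2 lesions by days of follow-up, and does so for T2 lesions in both cohorts.

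**The concern.** The percentage of participants with at least one event depends on how long they are watched as well as on the event rate. The overall column mixes two planned lengths of follow-up, and the mix is set by a voluntary decision at Month 18. Nothing in the plan makes that mix the same in the two cohorts, and nothing in the AE analysis corrects for it if it is not.

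There are reasons why it might differ. Protocol 4.5 expects no benefit for controls, while patients in the extension receive sponsor-supplied drug. Only treated patients are subject to the treatment-discontinuation rules in Protocol 9.1.1. These are reasons to plan for a difference; they are not evidence of one.

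At stake is how the ofatumumab and control columns are read side by side in the final report. Infections are the protocol's own example of what controls can inform. SAP 2.7.1.1 groups only injection site and injection systemic reactions, so a reader comparing infections will use the crude system organ class and preferred term rows.

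**Working it through.** **The plan's own figures.** The documents state no AE rate, extension uptake or follow-up by cohort, so there is no AE figure to reproduce. The one calculated design figure, NEDA-3 precision (SAP 3.1), does reproduce: 1.96 × √(0.80 × 0.20/100) = 7.8%, 1.96 × √(0.85 × 0.15/100) = 7.0%, and 100/0.85 = 117.6, rounded up to 118.

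**Inputs from the documents.** Follow-up of 18 months (1.5 years) without the extension and 30 months (2.5 years) with it; 118 ofatumumab and 50 control participants; 15% dropout allowed for in the ofatumumab sample size.

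**Assumptions.** The same constant event rate λ in both cohorts, and a share u of each cohort that enters the extension.

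**Formula.** P(t) = 1 − exp(−λt). Expected overall percentage = (1 − u) × P(1.5) + u × P(2.5). With equal rates, the gap between cohorts = (u_OMB − u_HC) × [P(2.5) − P(1.5)].

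**Results by event rate.**

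| λ per year | P(1.5) | P(2.5) | Overall, 80% v 30% uptake | Gap | Gap, 80% v 60% uptake |
|---|---|---|---|---|---|
| 0.1 | 13.9% | 22.1% | 20.5% v 16.4% | 4.1 | 1.6 |
| 0.3 | 36.2% | 52.8% | 49.5% v 41.2% | 8.3 | 3.3 |
| 0.5 | 52.8% | 71.3% | 67.6% v 58.3% | 9.3 | 3.7 |

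For λ = 0.3 the 80% v 60% gap is 0.20 × (52.8 − 36.2) = 3.3 points.

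**Results by 18-month incidence p18**, using P(30 months) = 1 − (1 − p18)^(30/18):

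| p18 | Gap, 80% v 60% | Gap, 80% v 40% |
|---|---|---|
| 5% | 0.6 | 1.3 |
| 10% | 1.2 | 2.4 |
| 20% | 2.2 | 4.4 |
| 30% | 3.0 | 5.9 |
| 50% | 3.7 | 7.4 |

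**Bounds and direction.** With equal uptake the gap is 0.0. If controls extend more often, the sign reverses: at p18 = 20% with uptake of 40% (ofatumumab) v 80% (controls), the gap is −4.4 points. The difference between 30-month and 18-month incidence is at most 18.6 points, near p18 = 54%, so the gap cannot exceed the uptake difference times 18.6 points.

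**The 5% threshold.** An event type with p18 = 3.5% has an expected overall percentage of 4.4% at 40% uptake and 5.3% at 80%. Uptake alone can therefore move it across the line if that table is run on the overall period.

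**Dropout within 18 months.** Suppose 15% drop out of one cohort only, evenly over the phase. A dropout's expected incidence is 1 − p18/(18λ), with λ here per month. At p18 = 20%, 18λ = 0.223, so this is 1 − 0.20/0.223 = 10.4%. The cohort figure falls by 0.15 × (20.0 − 10.4) = 1.4 points.

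**Does person-time remove the artefact?** At p18 = 20% the rate is −ln(0.80)/1.5 = 0.149 per year. First events divided by time at risk give 14.9 per 100 participant-years at both 80% and 40% uptake, while the crude percentages are 28.8% and 24.4%.

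**The case against.** The strongest reply is that the plan already contains a comparison of equal planned length. AEs are tabulated separately for the 18-month phase in both cohorts, and the Month 18 analysis is the primary one. This stands, and it confines the extension artefact to the final overall tables. Dropout inside the 18 months is still unadjusted, and the SAP never says that the 18-month table is the one to use for comparing cohorts.

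Second, follow-up by cohort is reported, so a difference would be visible. That is true, but a reader cannot convert a mean duration into a corrected percentage.

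Third, the comparative aim is modest. The safety objective in Protocol Table 2-1 and SAP Table 1 concerns ofatumumab alone, whereas the atrophy objective beside it names healthy controls. SAP 2.13 rules out testing and estimation at Month 30. This lowers the stakes, but the Protocol summary and section 1.2 still announce the comparison, and side-by-side percentages will be read as one.

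Fourth, sampling error is larger. At 20% incidence the standard error of the difference is √[0.20 × 0.80 × (1/118 + 1/50)] = 6.7 points. That is fair as to scale, but a follow-up bias adds to random error and no confidence interval shows it.

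Fifth, person-time rates have a weakness of their own. They assume a roughly constant hazard. Protocol 4.5 describes systemic injection reactions in the earlier phase 3 trials as limited to the first injection. For such front-loaded events, longer follow-up lowers the rate and could flatter the cohort watched longer. This stands and limits the remedy.

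A reader might also infer that the second consent falls on controls alone, since the Amendment 03 summary mentions "2 distinct time periods for healthy control arm since reconsenting after the first 18 months will be required". The current Table 8-1 marks it for both cohorts.

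**Conclusion.** The point holds as a conditional one. The final overall percentages are not adjusted for follow-up, and they will differ between cohorts with equal event rates if extension uptake or dropout differs. For rates of 0.1 to 0.5 per year, the extension artefact is about 1.6 to 3.7 points at 80% v 60% uptake and 4 to 9 points at 80% v 30%. For events near 5% incidence at 18 months it is 0.6 points at 80% v 60%. These sizes rest on a constant rate common to both cohorts and on assumed uptakes.

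Two stronger readings are tempting and are not supported. One is that follow-up will be unequal, to the disadvantage of ofatumumab. The extension is optional and separately consented in both cohorts and no uptake is given, so neither the inequality nor its direction is established. Continued drug supply is a weak argument for greater uptake among patients, because Protocol section 3 and 6.1.5 let them move to commercial drug. The other reading is that the whole safety comparison with controls is confounded. The 18-month tables and the Month 18 primary analysis are free of the extension artefact.

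What remains is a gap in the final reporting that is cheap to close.

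**What to change.** 1. State in SAP 2.7.1 that ofatumumab-versus-control safety statements rest on the 18-month open-label treatment phase, and that the overall percentages are not adjusted for follow-up.
2. For the by-cohort overall rows for any AE, system organ class (including infections) and serious AEs, add exposure-adjusted first-event incidence: participants with a first event per 100 participant-years at risk, with an exact Poisson 95% confidence interval. Time at risk ends at the first event or at the end of follow-up.
3. Note beside these rates that they assume a roughly constant hazard and are not suited to front-loaded events such as injection reactions. They should not be the sole basis for a cohort comparison.
4. Adjust SAP 2.13 so that descriptive intervals on the Month 30 rates do not contradict its statement that nothing is estimated then.

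The cost is SAP wording and some extra table columns, with no new data. The programming is more than a reuse of existing variables: the durations in SAP 2.4.1 run to last contact or data cut-off, so a separate time at risk must be derived for each event grouping from dates already collected.
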